9.5.3 Safety Endpoints

All reported adverse events will be categorized by system organ class and preferred term according to the Medical Dictionary for Regulatory Activities (latest version at the time of final analysis) dictionary and graded by CTCAE, version 4.03.

Safety analyses of the safety endpoints will be performed based on the Safety Analysis Set according to the actual treatment groups (switching group versus continued-use group). Treatment-emergent adverse events post randomization are defined as adverse events that start or worsen on or after the first dose of investigational product post randomization and prior to the EOS. The numbers and percentages of subjects reporting treatment-emergent adverse events, serious adverse events and events of interests will be tabulated by treatment group. The number and percent of subjects developing binding or neutralizing antidrug antibody (ADA) in the subset of Safety Analysis Set who have at least one ADA result post randomization will be tabulated descriptively by treatment group and by visit.

Laboratory data (hematology, serum chemistry, and urinalysis) will be converted to Système International units for reporting purposes. Absolute values and changes from week 12 for laboratory data post randomization will be summarized descriptively by treatment group and visit.

For vital signs post randomization, absolute values, and changes from week 12 will be summarized descriptively by treatment group and visit.

Physical examination values post randomization will be summarized descriptively by treatment group and by visit.

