9.5.4.2 Analyses for the Lead-in Period

All analyses for the lead-in period will be based on the Lead-in Treated Set.

Available serum concentrations over time will be summarized descriptively for each scheduled visit during the lead-in period.

Treatment-emergent adverse events during the lead-in period are defined as adverse events that start or worsen on or after the first dose of investigational product and prior to the first dose post randomization or EOS for lead-in failures.

The number and percentage of subjects reporting treatment-emergent adverse events, serious adverse events and events of interest during the lead-in period will be summarized.

The number and percentage of subjects developing binding or neutralizing ADAs during the lead-in period will be summarized.

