5.1 General

Actual Treatment Received During Lead-in Period

If a subject received any dose of ABP 501 during the Lead-in Period, the actual treatment for the subject is defined as ABP 501. Otherwise, the actual treatment for the subject is defined as Humira.

Actual Treatment Received During Post-randomization Period

For a subject randomized to switching group or continued use group and receiving all assigned treatments, the actual treatment received is defined as the switching group or the continued use group. Subjects randomized to the switching group that deviate from the switching regimen will be analyzed in a separate group and their actual treatment will be labeled "Deviated from Switching Regimen". Similarly, subjects randomized to the continued use group and deviate from this treatment regimen will be in actual treatment group labeled "Deviated from Continued use Regimen".

Baseline

Unless stated otherwise, the baseline of the study is defined as the last non-missing assessment taken prior to the first dose of investigational product (IP) a subject received (see definition of first dose date). In cases where baseline assessments are taken on the

Protocol Number: 20200497

Date: 10FEB2023 Page 13 of 36

same day as the first dose of IP, and either no times are reported or the IP and assessment times are the same, it will be assumed that these assessments are taken prior to IP being administered.

Change from Baseline

Change from baseline is defined as (value at post-baseline visit – value at baseline).

Concomitant and Prior Medication

Prior medications are defined as medications with a stop date prior to first dose of IP the subject received (see definition of first dose date). Concomitant medications are defined as any medications ongoing at the start of IP treatment for the subject or with a start date on or after the first dose date.

Developing ADA incidence

Developing antibody incidence during the Lead-in Period is defined as the number of subjects in the Lead in Treated Set (LTS) with a negative or no antibody result at baseline and a positive antibody result post-baseline (including unscheduled visits) during the Lead-in Period divided by the number of subjects in the LTS with at least one post-baseline result during the Lead-in Period.

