^a Safety lab is not scheduled at week 2 and week 16. Laboratory parameters assessment will not be included at these two visits in the output tables.

^b If a subject has laboratory measurements on the same day as the first dose date at week 1/Day 1 or week 12 but at a time after the first dose of IP at week 1/Day 1 or week 12, respectively is administered, the laboratory measurements will not be defined as baseline or week 12, but will be included in consideration for week 6 or 20 measurements, respectively.

Protocol Number: 20200497

Date: 10FEB2023 Page 15 of 36

PK concentrations between Week 28 – Week 30 are summarized by nominal study visit per the following table as listed in the protocol:

Tolerance Windows for Pharmacokinetic Endpoint Sample Collection

Study Visit	Tolerance Windows ^a
Week 28 predose	Within 3 hours prior to week 28 investigational product administration
1 hour post week 28 dose	±15 minutes
1 day post week 28 dose	±5 hours
3 days post week 28 dose	±6 hours
4 days post week 28 dose	±6 hours
7 days post week 28 dose	±6 hours
11 days post week 28 dose	±24 hours
14 days post week 28 dose	±48 hours

^a The week 28 visit and dose should be performed with a window of \pm 3 days. Subsequent visits are done in relation to the actual week 28 investigational product dose date (eg, for the 3 days post week 28 dose timepoint, the PK sample should be collected 3 days after the actual week 28 dose, with a collection window of \pm 6 hours). PK: pharmacokinetic(s)

For ADA

Study Analysis Visit	Target Day	Study Day
Baseline	1	<=1
Week 6	36	<=56
Week 12	78	<=91
Week 16	106	<=119
Week 20	134	<=161
Week 28	190	<=196
Week 30	14 days post week 28 dose	<=210
Week 32	218	<=EOS Visit Date

Study Day

Study day is defined as the number of days from Study Day 1.

Before Study Day 1: Study Day = (Date of assessment – Date of Study Day 1)

Protocol Number: 20200497

Date: 10FEB2023 Page 16 of 36

On or After Study Day 1: Study Day = (Date of assessment – Date of Study Day 1) +1

Therefore, the day prior to Study Day 1 is -1.

Study Day 1

Study day 1 is defined as the first day of IP the subject received (see definition of first

dose date).

Study Period

The following definitions will be used for PK, safety and efficacy analyses.

Lead-in Period

It is defined as the time period from the first dose of IP the subject received (see

definition of first dose date for the subject) until prior to the first post-randomization dose

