5.4 Safety

Adverse Events Leading to Discontinuation from IP/Study

Protocol Number: 20200497

Date: 10FEB2023 Page 19 of 36

AEs leading to discontinuation from IP/study are those with an action taken with IP indicating "drug withdrawn" or other action taken of "study discontinued".

Event of Interest (EOI)

An EOI is defined as a noteworthy event for a particular product or class of products that a sponsor may wish to monitor carefully. It could be serious or non-serious and could include events that might be potential precursors or prodromes for more serious medical conditions in susceptible individuals (Council for International Organizations of Medical Sciences [CIOMS] VI, 2005). The EOIs for this study will include:

- · Serious infections.
- malignancies,
- hypersensitivity reactions,
- demyelinating disease,
- hematological reactions,
- heart failure,
- lupus-like syndrome,
- liver enzyme elevations,
- and injection site reaction.

The detailed search strategies for the EOIs are included in Appendix A.

Treatment-emergent Adverse Event

Treatment emergent adverse events (TEAEs) during the Lead-in Period are defined as adverse events that start on or after the first dose of IP and prior to the first dose post randomization for randomized and treated subjects, or EOS for lead-in failures or for subjects who were randomized but not treated post-randomization.

TEAEs during the Post-randomization Period are defined as adverse events that start on or after the first dose of IP post-randomization and prior to the EOS.

If the adverse event starts on the same day as the first dose of IP, then the flag indicating whether the adverse event started prior to the first dose on the adverse event CRF page will be used to determine whether this is a TEAE during the Lead-in Period. For randomized and treated subjects, an adverse event that starts on the same day as the first post-randomization dose will be considered as a TEAE post-randomization.

Protocol Number: 20200497

Date: 10FEB2023 Page 20 of 36

6. Analysis Sets

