9.7.2 Laboratory Test Results

Laboratory data (hematology, serum chemistry, and urinalysis) will be converted to Système International units for reporting and processing purposes.

For the Post-randomization Period, absolute values and changes from baseline by visit will be presented descriptively. In addition, shift tables of the worst post-randomization laboratory toxicity based on CTCAE grading relative to randomization at week 12 will be presented. The shift tables will take into account all post-randomization (schedule and unscheduled) laboratory results in the determination of the worst post-randomization laboratory toxicity. Furthermore, subject incidence tables of grade ≥ 3 laboratory toxicities will be provided. Standard ranges will be used for the laboratory analysis.

For the Lead-in Period, absolute values and changes from baseline by visit will be presented descriptively.

Lab assessments will be grouped for summary as follows:

Hematology: white blood cell parameters: white blood cell count and differential,

Hematology: red blood cell parameters: hemoglobin, hematocrit, red blood cell count, absolute neutrophil count,

Hematology: other parameters: platelets,

Serum chemistry: hepatobiliary parameters: alanine aminotranferase (ALT), aspartate aminotransferase (AST), total bilirubin, alkaline phosphatase, gamma glutamyl transferase,

Serum chemistry: general chemistry: sodium, potassium, albumin, total protein, glucose (random),

Serum chemistry: renal function tests: blood urea nitrogen, creatinine,

Urinalysis: pH, specific gravity, glucose, bilirubin, blood, and protein.

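### The SAP takes post-randomization lab and vital-sign changes from study baseline instead of week 12 and drops worsening from both TEAE definitions, without listing either change

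*SAP*

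**What the plan says.** **Reference visit.** For laboratory data, protocol 9.5.3 asks for "Absolute values and changes from week 12 for laboratory data post randomization". For vital signs it says "For vital signs post randomization, absolute values, and changes from week 12 will be summarized descriptively by treatment group and visit". SAP 9.7.2 instead says "For the Post-randomization Period, absolute values and changes from baseline by visit will be presented descriptively", and SAP 9.7.3 does the same for vital signs. SAP 5.1 says, unless stated otherwise, that "the baseline of the study is defined as the last non-missing assessment taken prior to the first dose of investigational product", and neither 9.7.2 nor 9.7.3 states otherwise.

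**TEAE definition.** For the post-randomization period, protocol 9.5.3 counts "adverse events that start or worsen on or after the first dose of investigational product post randomization". For the lead-in, protocol 9.5.4.2 counts "adverse events that start or worsen on or after the first dose of investigational product and prior to the first dose post randomization". SAP 5.4 uses onset alone in both periods; for the later one it says "TEAEs during the Post-randomization Period are defined as adverse events that start on or after the first dose of IP post-randomization". Its rules for events on a dosing day also refer only to onset.

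**Disclosure.** SAP section 10, which is the place for departures from the protocol's analyses, covers only the PK Parameter and Per-protocol PK Parameter Analysis Sets.

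**The concern.** The trial asks what happens to patients who are switched after week 12, compared with patients who are not. Week 12 is the natural zero for a post-randomization change. A programmer who follows the SAP will produce changes from Day 1, which mix the lead-in with the period of interest.

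Post-randomization TEAEs are a named secondary endpoint. An event that began in the lead-in and became more severe after a switch is something the protocol says it will count. Under the SAP wording it could stay assigned to the lead-in.

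Because section 10 does list one set of changes, its silence on these two will be read as meaning that there are no others.

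**Working it through.** There is no stated figure to reproduce. The check is a comparison of text plus simple day counts.

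| Output | Protocol | SAP |
|---|---|---|
| By-visit lab change after randomization | from week 12 (9.5.3) | from study baseline (9.7.2) |
| Lab toxicity shift | not specified | from week 12 (9.7.2) |
| By-visit vital-sign change after randomization | from week 12 (9.5.3) | from study baseline (9.7.3) |
| TEAE, post-randomization | start or worsen (9.5.3, also the synopsis) | start (5.4) |
| TEAE, lead-in | start or worsen (9.5.4.2) | start (5.4) |

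**1. Is 'baseline' in SAP 9.7.2 and 9.7.3 loose wording for week 12?** No. The SAP 5.1 visit table lists the two as separate visits, and its footnote on same-day post-dose samples says "the laboratory measurements will not be defined as baseline or week 12". SAP 9.7.2 also names week 12 when it means it, in the shift tables.

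**2. What does the change contain?** With Y(t) the value at day t and the SAP 5.1 target days (baseline 1, week 12 78):

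Y(t) − Y(1) = [Y(t) − Y(78)] + [Y(78) − Y(1)]

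The second bracket is the lead-in change over 78 − 1 = 77 days. At week 16 (day 106) the SAP interval is 106 − 1 = 105 days, against 106 − 78 = 28 days under the protocol. At week 32 (day 218) it is 217 days against 140.

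**3. Which visits are affected?** From protocol Table 1-1:
- vital signs: all five post-randomization visits (weeks 16, 20, 28, 30 and 32);
- hematology and chemistry: both post-randomization visits (weeks 20 and 32);
- urinalysis: scheduled only at screening, baseline and week 32, so the protocol's week-12 reference cannot be applied to it.

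**4. Can the existing week-12 analysis visit serve as the reference?** Not by itself. Its window is days 57 to 91, it admits unscheduled visits, it takes the value nearest day 78, and it resolves ties in favour of the later value. As an illustration, take a subject assessed and dosed on day 75 with an unscheduled value on day 77. The distances from target are 3 days and 1 day, so the post-dose value is chosen. The footnote removes only same-day post-dose laboratory values.

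**5. Is a worsening lead-in event lost?** That depends on how it is recorded.
- Towards a new record: protocol 8.2.1, 8.3.1.1 and 8.3.1.1.1 treat worsening or exacerbation as reportable.
- Towards the old record: protocol 8.3.4.5 sends updated information on a serious event to the form first completed for it, though it does not mention worsening.
- Protocol 8.3.4 lists onset and resolution dates among the attributes, but no date of grade change.
- No section says what happens to an event still ongoing at week 12.

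If no new record is opened, onset stays in the lead-in. SAP 9.7.1 gives the lead-in no preferred-term table of grade 3 or higher events, of discontinuations or of dose delays, so the worsened event would appear in none of those tables for either period. Serious events would still appear in the lead-in serious-event tables.

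For the lead-in definition the omission matters little. Earlier non-serious events are medical history (Table 1-1, footnote c), and their exacerbation is itself an adverse event.

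**The case against.** The strongest reply is that little is lost.
- The lab and vital-sign changes are descriptive and are not among the safety endpoints of either document.
- For labs, SAP 9.7.2 keeps shift tables against week 12, incidence tables for grade 3 or higher and absolute values by visit.
- For vital signs, observed values are still tabulated, and protocol 8.2.2 has clinically relevant abnormal findings reported as adverse events.
- The TEAE half rests on case report form practice that the documents do not show, and the visible text leans towards reporting worsening.

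All of this stands, and it limits the weight of the point. It does not remove the conflict, supply a week-12 change for vital signs, or explain the silence of section 10.

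Three stronger readings are tempting, and the documents support none of them:
- A reader might infer that most of the week-16 signal is lost, because 77 of 105 days precede randomization. That is a share of elapsed time. It says nothing about how much of any change in a value occurred before week 12.
- A reader might infer a biased comparison. Randomization is at week 12, so the lead-in term has the same expectation in both arms and cancels from the contrast. Its variance may change, but the documents give no figures from which to compute that.
- A reader might infer that post-randomization TEAEs are certainly undercounted. They are undercounted only if worsening does not open a new record.

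**Conclusion.** The concern holds as two undisclosed departures from the protocol with modest consequences.

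The reference-visit departure is certain. Following the SAP gives Day-1 changes, so within-arm summaries include the lead-in change, and vital signs have no week-12 change at all. The size in clinical units cannot be computed from the documents.

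The TEAE departure is certain in wording and conditional in effect. The number of events missed depends on how worsening is recorded and on how many events are ongoing at week 12. Neither is given, and the number may be zero.

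The statement that the contrast is unbiased in expectation assumes that the groups compared are essentially those randomized; SAP 5.1 places regimen deviators in separate groups. The primary PK analysis does not use any of these outputs.

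**What to change.** 1. **SAP 9.7.2 and 9.7.3.** For post-randomization changes in hematology, chemistry and vital signs, use the week-12 value, defined as the last non-missing value before the first post-randomization dose. Do not rely on the day 57 to 91 window alone. Untimed same-day values can follow the convention that SAP 5.1 already applies to baseline. Keep study baseline for urinalysis and state why.
2. **SAP 5.4.** Restore *start or worsen* in both definitions. State that worsening is identified from a new adverse event record, or from whatever grade-change data the case report form holds. If the form supports neither, say so in section 10.
3. **SAP section 10.** List and justify any departure that is intended.

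The cost is low for the first item: the week-12 measurements are already scheduled, and SAP 5.1 already defines the first post-randomization dose date, so only minor reprogramming is needed. The second item is a wording change if worsening opens a new record. If it does not, worsening may not be programmable, and disclosure in section 10 is what remains. The third is a few sentences.

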4.4 End of Study Definition

A subject is considered to have completed the study if he/she has completed all phases of the study including an EOS Visit or the last scheduled procedure shown in the Schedule of Assessments (Table 1-1). An EOS visit will be performed for subjects who are prematurely discontinued. All procedures listed under EOS visit must be completed for subjects who are prematurely discontinued.

The EOS is defined as the date of the last visit of the last subject in the study or last scheduled procedure shown in the Schedule of Assessments (Table 1-1) for the last subject in the study globally.

5 Study Population

The study population will consist of subjects with moderate to severe Ps (See Section 4.2 for details on rationale). Subjects (or legally acceptable representative) must be able to provide written consent and subjects must meet all the inclusion criteria and none of the exclusion criteria.

Approximately 414 subjects will be enrolled. Randomization will be stratified by prior biologic use for psoriasis at baseline (week 1/day 1, yes vs. no) and geographic region. Subjects with prior biologic use for psoriasis will be capped at 50% of the total enrolled subjects.

The number of subjects enrolled may be adjusted during the study with the actual lead-in failure rate seen to ensure approximately 342 subjects will be randomized at week 12.

5.1 **Inclusion Criteria**

Subjects cannot be enrolled before all the inclusion criteria (including test results) are confirmed. Subjects are eligible to be included in the study only if all of the following criteria apply:

1. Subject is male or female and is ≥ 18 and ≤ 75 years of age inclusive, at the time of enrollment.

Clinical Study Protocol: 20200497

Final 1.0 Date: 03 Jun 2021 Page **26** of **87**

2. Subject has moderate to severe Ps (with or without psoriatic arthritis) for at least 6 months and has stable disease for at least 2 months (eg, no morphology changes or significant flares of disease activity in the opinion of the investigator).

- 3. Subject has a score of PASI ≥ 12, involvement of ≥ 10% body surface area (BSA) and static Physician's Global Assessment (sPGA) ≥ 3 at screening and at baseline.
- 4. Subject is a candidate for phototherapy or systemic therapy, when other systemic therapies are clinically less appropriate.

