8.3.4 Documenting and Reporting of Adverse Events

The investigator is responsible for ensuring that all adverse events observed by the investigator or reported by the subject that occur from the time of enrollment through the EOS Visit are recorded in subject's medical records as well as the applicable CRF Adverse Event Summary page. The adverse event grading scale to be used for this study will be CTCAE version 4.03, as described in Section 8.3.2.1.

The investigator must assign the following adverse event attributes:

- Adverse event diagnosis or syndrome(s), if known (if not known, signs or symptoms)
- Dates of onset and resolution
- Severity (National Cancer Institute CTCAE version 4.03)
- Assessment of relatedness to investigational product, other protocol required therapies or devices
- Action taken

The investigator must assess whether the adverse event is possibly related to the investigational product. This relationship is indicated by a "yes" or "no" response to the question: "Is there a reasonable possibility that the event may have been caused by the investigational product?" The investigator is responsible for reviewing laboratory test results and determining whether an abnormal value in an individual study subject represents a clinically significant change from the subject's baseline values. In general, abnormal laboratory findings without clinical significance (based on the investigator's judgment) are not to be recorded as adverse events. However, laboratory value changes that require treatment or adjustment in

Clinical Study Protocol: 20200497 Final 1.0 Date: 03 Jun 2021

current therapy are considered adverse events. Where applicable, clinical sequelae (not the laboratory abnormality) are to be recorded as the adverse event.

The investigator's clinical judgment is used to determine whether a subject is to be removed from treatment due to an adverse event. A subject, or subject's legal representative, can also voluntarily withdraw from treatment due to an adverse event. If the subject withdraws consent, the subject is encouraged to undergo, at a minimum, an EOS assessment.

It is the investigator's responsibility to review all documentation (eq. hospital notes, laboratory reports, and diagnostic reports) related to an adverse event. Wherever possible, the investigator's diagnosis, not the individual signs and symptoms, will be documented as the adverse event

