8.3.4.1 Reporting of Serious Adverse Events

The investigator is responsible for ensuring that all serious adverse events observed by the investigator or reported by the subject that occur after signing of the ICF through the EOS Visit are reported using the applicable CRF Adverse Event Summary page or via the paper serious adverse event report form for serious adverse events occurring during screening for subjects not enrolled.

All serious adverse events must be documented, recorded, and transmitted to Amgen, or its designee, within 24 hours following the investigator's knowledge of the event.

Clinical Study Protocol: 20200497

Final 1.0 Date: 03 Jun 2021 Page **54** of **87**

The investigator will submit any updated serious adverse event data to the sponsor or designee within 24 hours of it being available.

The criteria for grade 4 in the CTCAE grading scale differs from the regulatory criteria for serious adverse events. It is left to the investigator's judgment to report these grade 4 abnormalities as serious adverse events.

If the electronic data capture (EDC) system is not functional, the serious adverse event can be reported by faxing a completed paper Serious Adverse Event Form to the fax number as indicated on the SAE form or by direct telephone communication with Amgen or its designee. The event must be updated electronically in the EDC system by the clinical study center once the EDC function resumes.

After the study is completed at a given center, the EDC system will be taken off-line to prevent the entry of new data or changes to existing data. If a center receives a report of a new serious adverse event from a study subject or receives updated data on a previously reported serious adverse event after the EDC has been taken off-line, then the center can report this information on a paper Serious Adverse Event Form.

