Developing antibody incidence during the Post-randomization Period is defined as the number of subjects in the Safety Analysis Set (SAS) who have a positive result post randomization and have never tested positive (i.e., negative or no results) prior to the first dose of post-randomization IP divided by the number of subjects in the SAS who have at least a result post randomization.

End of Study (EOS) Date

The EOS date is the date recorded on the End of Study page of the CRF.

First Dose Date

It is defined as the date the subject received the first dose of IP.

First Post-randomization Dose Date

It is defined as the date the subject received the first post-randomization dose of IP.

Last Dose Date

It is defined as the date the subject received the last dose of IP.

Last Observation Carried Forward (LOCF)

Protocol Number: 20200497

Date: 10FEB2023 Page 14 of 36

A method of imputation where missing post-baseline data will be imputed by carrying forward the last non-missing post-baseline value for that endpoint. Baseline values will not be carried forward.

Neutralizing ADA Negative Subgroup

Defined as subjects in the subset of Safety Analysis Set (SAS) who have never tested positive (i.e. tested negative or no results) prior to the first dose of post-randomization IP, have at least one neutralizing ADA result post-randomization, and all available post-randomization neutralizing ADA results are negative.

Non Responder Imputation (NRI)

A method of imputation where a subject with missing post-baseline binary response data will be imputed as a non-responder, regardless of the reasons for missing data.

Study Analysis Visit

If more than one actual visit (including the unscheduled visits) falls within the same defined window, the visit closest to the target day with non-missing data will be considered for analysis. If two actual visit dates are at the same distance from the target day, the later visit with non-missing data will be considered for analysis.

For Efficacy, Vital, Safety Lab & PK

					Endpoint	
Study Analysis Visit	Target Day	Study Day	Interval (days)	Efficacy	Vital & Safety Labª	PK
Baseline ^b	1	≤1	NA	Х	Х	Х
Week 2	8	2-21	20		X	
Week 6	36	22-56	35	Χ	X	Χ
Week 12 ^b	78	57-91	35	Χ	X	Χ
Week 16	106	92-119	28	Χ	X	Χ
Week 20	134	120-161	42	Χ	X	Χ
Week 28	190	162-196	35		X	Χ
Week 30	14 days post week 28 dose	197-210	14	Х	Х	
Week 32	218	≥211	NA		Χ	

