for subjects who are randomized and treated post-randomization, or to the EOS visit for

subjects not randomized or for subjects who were randomized but not treated post-

randomization.

Post-randomization Period

For subjects who are randomized and treated post-randomization, it is defined as the

time period from the first post-randomization dose to the EOS visit.

Study Randomization

Study randomization is defined as when subject receives a random treatment allocation

via the IXRS system.

Total IP Exposure Duration

The total IP exposure duration for the subject (in weeks) for each study period (Lead-in

Period, Post-randomization Period) will be derived as: (the period end date - the period

start date+1)/7. The Lead-in Period end date for the subjects who are randomized and

treated post-randomization is the date of the first IP post randomization -1.

Transient ADA

A transient ADA result during the Lead-in Period is defined as a positive antibody result

post-baseline (including unscheduled visits) during the Lead-in Period with a negative or

no antibody result at baseline and a negative result at the subject's last visit tested within

the Lead-in Period.

Protocol Number: 20200497

Date: 10FEB2023 Page 17 of 36

A transient ADA result during the Post-randomization Period is defined as a positive antibody result post-randomization (including unscheduled visits) during the Post-randomization Period with negative or no antibody results prior to the first dose of post-randomization IP and a negative result at the subject's last visit tested within the Post-randomization Period.

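### AEs with onset on a subject's End of Study date are collected, but SAP 5.4 does not class them as treatment-emergent, so they reach no AE summary

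*SAP*

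**What the plan says.** SAP 5.4 defines post-randomization TEAEs as "adverse events that start on or after the first dose of IP post-randomization and prior to the EOS". In the lead-in period, the window for lead-in failures, and for subjects randomized but never dosed afterwards, also closes before the EOS. For randomized and treated subjects it closes before the first post-randomization dose. The section gives same-day rules for the two first-dose days and none for the EOS day.

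SAP 5.1 fixes the date per subject: "The EOS date is the date recorded on the End of Study page of the CRF". For treated subjects it defines the Post-randomization Period as the "time period from the first post-randomization dose to the EOS visit".

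The bound comes from the protocol. Protocol 9.5.3 counts events that "start or worsen on or after the first dose of investigational product post randomization and prior to the EOS", and 9.5.4.2 uses EOS as the limit for lead-in failures. (The SAP's omission of worsening events is a separate matter.) The collection rules are wider. Protocol 8.3.4 covers AEs "that occur from the time of enrollment through the EOS Visit are recorded", and 8.3.4.1 covers SAEs "that occur after signing of the ICF through the EOS Visit are reported". Protocol 4.4 also gives the term a study-level meaning: "The EOS is defined as the date of the last visit of the last subject in the study".

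**The concern.** The TEAE window is one day shorter than the collection window and the study period it is meant to summarize. Post-randomization TEAEs, SAEs and EOIs are the secondary safety endpoints, and every AE output in SAP 9.7.1 depends on treatment-emergent status. An AE or SAE with onset on the EOS date would be recorded by the site and then left out of the tables by a strict inequality. Neither document gives a reason for leaving that day out. It is also a day with a full set of scheduled safety assessments, and clinically significant findings from these are to be reported as AEs (protocol 8.2.1, 8.3.1.1.1).

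**Working it through.** There is no stated figure to reproduce. The check sets the rules side by side and applies them to the planned days.

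**1. Is the EOS day included?**

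| Rule | EOS day |
|---|---|
| TEAE window, SAP 5.4 | Excluded |
| AE and SAE collection, protocol 8.3.4 and 8.3.4.1 | Included |
| Post-randomization Period, SAP 5.1 | Runs to the EOS visit; the exposure formula (end − start + 1)/7 counts the end day |
| ADA week 32 window, SAP 5.1 | Included (at or before the EOS visit date) |

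Only the TEAE window leaves the day out.

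**2. The rule on planned days.** Inputs are the SAP 5.1 target days: week 12 = day 78 and week 32 = day 218. Assume that the CRF End of Study date equals the week 32 visit.

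- Current rule: 78 ≤ onset < 218. Onset on day 217 is a TEAE; onset on day 218 is not.
- Inclusive rule: 78 ≤ onset ≤ 218. Both are TEAEs.
- Period length: 218 − 78 + 1 = 141 days (141/7 = 20.1 weeks). Share excluded: 1/141 = 0.7%.

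**3. What is scheduled that day (protocol Table 1-1).**

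- Physical examination and urinalysis: screening, baseline and EOS. The EOS assessment is the only one after baseline.
- Hematology and chemistry: after the first post-randomization dose, week 20 and EOS, so 1 of 2 draws. The week 12 draw precedes dosing.

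**4. Which outputs lose the event (SAP 9.7.1).** Summaries (a) to (n) cover overall, SAE, fatal, EOI and COVID-19 events, and all are restricted to treatment-emergent events. So is the SAE listing.

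**5. Lead-in failures.** SAP 3.1 has non-responders complete EOS procedures at week 12. Their only scheduled physical examination and urinalysis after baseline then fall at the EOS visit, which is on the excluded day if the CRF date is the visit date. The plan allows for 414 − 342 = 72 lead-in failures of all kinds.

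**The case against.** The strongest objection concerns the word EOS. Protocol 4.4 defines it at study level, and protocol 10.1.5.3 and 10.1.10 give the EOS date in the same sense. On that reading almost no event is lost. This does not rescue the rule. Both documents use EOS as a per-subject limit for lead-in failures, and the SAP supplies a CRF-based date for each subject. It does show that the term needs reconciling.

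Other points stand and limit the finding:

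- A reader might infer that findings from the last laboratory draw disappear. They do not. SAP 9.7.2 gives by-visit summaries, shift tables on all post-randomization results and grade ≥ 3 incidence tables, none tied to TEAE status. Only the AE record is lost.
- A reader might infer that any death on the EOS date is lost. TEAE status follows the onset date, so a death that day from an AE that began earlier is still a fatal TEAE. Only a fatal AE with onset on that date drops out, and a study discontinuation due to death would still appear in the disposition summary (SAP 9.2).
- A reader might infer that anything found at week 32 is never a TEAE. The investigator records the onset date, and an event first reported at week 32 that began earlier counts. If the CRF date is later than the visit, visit-day events also count.
- The counts in step 3 are of procedures, not events. AEs are recorded at 16 scheduled contacts from week 12 to week 32, of which EOS is one.
- The rule is the same in both groups, safety is assessed descriptively, and the primary PK conclusion is untouched.
- The wording originates in the protocol, so changing it departs from the protocol definition.

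**Conclusion.** The point holds in a limited form. On the SAP's own definitions, an AE with onset on the subject's EOS date is collected, lies inside the Post-randomization Period, and is left out of every AE summary and the SAE listing. The same holds at the end of the lead-in window for lead-in failures and for subjects randomized but not treated.

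The window lost is 1 of 141 planned days. The number of events is not estimable from the documents and is probably small. Nothing in them supports a claim of bias between arms. The link to the final examination, urinalysis and laboratory draw rests on two assumptions that the documents do not settle: that the CRF End of Study date equals the EOS visit date, and that the finding is given that date as its onset. The correction is still worth making, because it concerns secondary safety endpoints and the current rule conflicts with the collection window, the study period and the ADA window.

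**What to change.** In SAP 5.4, for the Post-randomization Period and for lead-in failures and subjects randomized but not treated, let the window include events that start *on or before the subject's EOS date (End of Study CRF page)*. Keep the existing limit at the first post-randomization dose for randomized and treated subjects in the lead-in period, so that no event is counted in both periods. State that the subject-level date applies and not the study-level EOS of protocol 4.4. Record the change in SAP section 10 as a departure from protocol 9.5.3 and 9.5.4.2. Check also that the CRF date cannot precede the EOS visit; if it can, even an inclusive bound would stop short of the collection window.

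The cost is a phrase in the SAP and one inequality in the programming, with no new data. TEAE counts may rise slightly in both groups.
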